### **Primary Endpoints and Data Analysis Plan**

The primary endpoints include change in MVPA and sedentary time during recess measured by accelerometry. The secondary outcome includes change in fundamental motor skills.

Statistical analyses will be performed with the latest version of SAS. Means, standard deviations, and Pearson correlations will be calculated to describe the sample and examine differences between the intervention and control group. Differences in center characteristics (e.g. racial distribution of participants) will be tested using t-tests and chi-square tests. A repeated measures ANCOVA model will be used to test for effects of playground stenciling on each dependent continuous variable (minutes/recess MVPA, minutes/day MVPA in childcare center, minutes/recess Sedentary behavior, minutes/day Sedentary behavior in childcare center, minutes/day MVPA total, minutes/day screen-time total). T-tests and chi-square tests will be used to determine whether changes in outcome variables were different between the intervention and control childcare centers. Covariates will include age, sex, BMI z-score, and sociodemographic characteristics.

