The aim will be achieved through a pilot project that is grounded in rigorous and reproducible methodology, meaning the results can be generalized to other parts of the state and held as a model throughout the country. We expect that children who attend the childcare center that receives the stenciling will have greater increases in moderate to vigorous physical activity (MVPA) and fundamental motor skill competency, and larger decreases in sedentary behavior, compared to children who attend the control facility (who will receive the stencils after an approximate 6 to 8-week delay). The main outcome variable will be percentage of recess time spent in MVPA, measured objectively using a physical activity monitor (i.e. accelerometer). Additional outcome variables include fundamental motor skill competency, measured using the validated Test of Gross Motor Development (TGMD-3; Ulrich, 2016), and the percentage of recess spent being sedentary (accelerometry). Parents will provide demographics of all consented children, and height and weight will be collected before and after the intervention. We do not expect changes in weight status during this short time period but will include obesity as a covariate to control for differences in MVPA that may be due to weight.

This project will test the effectiveness of a promising (cost-effective, easily scalable) playground stenciling intervention in order to validate the need for dissemination to numerous childcare centers across Louisiana. Ultimately, this pilot may launch an innovative strategy that has the potential to disrupt negative trends in obesity and sedentary behavior among Louisiana preschoolers.

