## Recruitment Methods

All parents of children between the ages of 3-6 years at the 4 selected childcare centers will receive an informational handout/flyer and consent form to participate in study procedures. Informational materials about the study may also be distributed to parents via email, mail, fax, phone, or in-person through the school. Children for whom a completed consent form is returned by their parent or legal guardian will be eligible to participate. We aim to recruit up to 72 children (18 per center) between August 2018 and February 2019.

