## Procedures

Below are the procedures that will be completed during study participation (Table 2).

Table 2: Procedures and Timeframes				
	Baseline Intervention Center	Baseline Control Center	Follow-up Intervention Center	Follow-up Control Center
Consent	X	X		
Parent Survey	X	X		
Height	X	X	X	X

Weight	X	X	X	X
TGMD-3 (Motor Skills)	X	X	X	X
Actigraph (Physical Activity)	X	X	X	X
Ages and Stages (Motor Skills Questionnaires – 4 yr olds only)			X	X
activPAL (Physical Activity – 4 yr olds only)			X	X
Card Sort, Go/No-Go, [name] (Cognitive/Executive Function Tests – 4 yr olds only)			X	X

Parent survey. Parents will be asked to complete a questionnaire that will provide information on the child's sociodemographic characteristics, including sex, date of birth, and parents' marital status, highest level of education, family income, occupation, employment status, and the child's physical activity, sedentary time, screen time and sleep time. There are also questions pertaining to electronic screen device use by the parent/caregiver with the child. The final sections asks about the child's sedentary travel time and time spent outside. The poverty guidelines developed by the Department of Health and Human Services will be used as our measure of socioeconomic status. The child's movement behaviors are designed to align with the forthcoming WHO Guidelines. The questionnaire should take 15-20 minutes for the parent to complete.

COVID-19 Survey. Parents will be asked to complete a version of the Parent Survey related to the stay at home order that families were under due to the COVID-19 pandemic. The survey will be administered by phone when possible, and will be sent out via email using REDCap as an alternative.

Anthropometric measurements. Height and weight of each child will be measured in a private setting with children dressed in light clothing. Height will be measured to the nearest 0.1 cm using a SECA portable stadiometer. The measure will be repeated and if the two measures differ by more than 0.5 cm a third measurement will be recorded. Weight will be measured to the nearest 0.1 kg using a SECA electronic scale. The measurement will be repeated and if the two measures differ by more than 0.25 kg a third measurement will be recorded. Body mass index (BMI) z-score will be calculated based on the child's age, sex, height, and weight, then compared to the 2000 Centers for Disease Control and Prevention (CDC) Growth Charts.

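### Stencils are assigned to whole childcare centers (four in all), but the effect is tested with no center term, so type I error exceeds 5% by an amount set by an unstated ICC

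*Combined protocol and SAP*

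**What the plan says.** **Assignment.** Objectives, A. Specific Aims expects that "children who attend the childcare center that receives the stenciling will have greater increases" "compared to children who attend the control facility", which is stenciled 6 to 8 weeks later. Under Vulnerable Populations, each director gives permission for the stencils. The stencils are therefore assigned to centers, not to children.

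**Numbers.** Recruitment Methods addresses "All parents of children between the ages of 3-6 years at the 4 selected childcare centers" and states: "We aim to recruit up to 72 children (18 per center) between August 2018 and February 2019". It does not say how many centers are in each arm. Specific Aims writes of one stenciled center and one control facility, and the column headings of Table 2 (Procedures) are also singular, for example "Baseline Intervention Center".

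**Analysis.** The Primary Endpoints and Data Analysis Plan section says "A repeated measures ANCOVA model will be used to test for effects of playground stenciling on each dependent continuous variable". It continues: "T-tests and chi-square tests will be used to determine whether changes in outcome variables were different between the intervention and control childcare centers". On adjustment it says: "Covariates will include age, sex, BMI z-score, and sociodemographic characteristics". The text supplied for review contains no center effect, mixed model, cluster-robust variance, design effect or ICC. The unit of analysis is not named.

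**The concern.** Children at one center are likely to share a playground, staff, recess schedule and weather, and the primary endpoints are measured during recess. If a center's recess is lengthened, moved indoors or supervised differently between baseline and follow-up, all its children can shift together. A child-level test treats that shift as many independent observations. When the shift differs between arms, it is read as a stencil effect.

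The repeated measures part of the model handles two measurements on the same child. It does nothing about children who share a center. The test of center characteristics in the same section is descriptive and does not correct the intervention test.

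This is the test of the study's only aim, on its primary endpoints. Specific Aims intends the result to support wider dissemination in Louisiana and says it can be generalized. An ordinary difference between centers could be reported as effectiveness.

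**Working it through.** **Inputs from the documents.** There are 4 centers with m = 18 children each, and 4 × 18 = 72, which matches the stated total. No power calculation is given, so there is none to reproduce.

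**Assumptions.** The documents give no significance level, ICC, SD or split. I take a two-sided 5% level, full enrolment, effects in SD units of change, and an ICC of the change score from 0 to 0.20. The main case is two centers per arm.

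**Degrees of freedom.** Center-level df = 4 − 2 = 2 for a 2 v 2 or a 1 v 3 split. The child-level test uses 72 − 2 = 70. The critical t values are 4.303 and 1.994.

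**Formulas**
- Design effect: DE = 1 + (m − 1) × ICC = 1 + 17 × ICC.
- Approximate true type I error of the child-level test: 2 × [1 − Φ(1.96/√DE)].
- Child-level 95% half-width: 1.994 × √(2/36) = 0.47 SD (slightly less, down to about 0.44, as the ICC rises).
- Mean center-level 95% half-width: 4.303 × √(2 × DE/36) × 0.886, where 0.886 is the mean of the estimated SD over the true SD on 2 df.
- Effect detectable with 80% power (a conventional target, not one in the plan): 2.84 × √(2/36) = 0.67 SD at child level, and 5.66 × √(2 × DE/36) at center level.

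**Example, ICC 0.05.** DE = 1 + 17 × 0.05 = 1.85. Type I error ≈ 2 × [1 − Φ(1.96/√1.85)] = 0.150. Half-width = 4.303 × √(2 × 1.85/36) × 0.886 = 1.22 SD. Detectable effect = 5.66 × 0.3206 = 1.81 SD.

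| ICC of change | DE | Type I error, formula | Type I error, simulated t-test (2 v 2) | Center-level half-width, SD | Detectable effect at center level, SD |
|---|---|---|---|---|---|
| 0 | 1.00 | 5.0% | 5.0% | not run | 1.33 |
| 0.01 | 1.17 | 7.0% | 7.1% | 0.97 | 1.44 |
| 0.05 | 1.85 | 15.0% | 15.2% | 1.22 | 1.81 |
| 0.10 | 2.70 | 23.3% | 24.0% | 1.48 | 2.19 |
| 0.20 | 4.40 | 35.0% | 37.1% | 1.88 | 2.80 |

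The simulated column rests on 200,000 null trials per ICC. With two occasions, the arm-by-time test is a comparison of changes, so the t-test on change is the natural reference. In the same trials, a t-test on center means (2 df) rejected 5.0% of the time at each ICC from 0.01 to 0.20.

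**Variations (ICC 0.01 / 0.05 / 0.10 / 0.20)**
- 1 v 3 split: type I error 7.0 / 15.3 / 24.1 / 37.0%; center-level half-width 1.12 / 1.41 / 1.70 / 2.18 SD.
- ANCOVA with four covariates unrelated to the center effect: 6.6 / 14.4 / 22.6 / 35.1%.
- ANCOVA where one covariate (assumed to have 30% of its variance between centers) tracks half of the center variance: 6.7 / 12.5 / 19.7 / 32.5%.
- 14 analyzable children per center: 6.6 / 13.0 / 20.2 / 32.2%.
- One center per arm: 7.0 / 15.4 / 24.9 / 39.2% with 18 children each, or 9.1 / 24.5 / 37.6 / 53.3% with 36 each. Center-level df are 0, so the stencil effect cannot be separated from the center.

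**A trap in the remedy.** With 2 v 2, the center variance is estimated as zero in 57 / 40 / 28 / 17% of trials. If the software then drops the term and reverts to 70 df, the error in those trials is still about 7 / 16 / 25 / 39%.

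**The case against.** The strongest reply is that the harm depends on an unknown. The relevant ICC is that of change, which may be well below the ICC of a single measurement; at zero the plan's test is exact, and at 0.01 the inflation is mild. That stands, and the conclusion is conditional on it. It does not rescue the plan, because four centers cannot show that the ICC is negligible.

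Two further points lower the figures without changing their direction. The ANCOVA rates are a little below the t-test rates, and full enrolment is the upper end of a target of up to 72. Both are shown above.

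The singular wording in Specific Aims and Table 2 may be generic labelling. That is plausible, since 4 centers of 18 agree with the total of 72. The type I error result does not need the point, as 2 v 2 and 1 v 3 agree, but the split still has to be stated.

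The t-test sentence could be read as comparing center mean changes. If so, it has 2 df and is close to the remedy below, but the plan does not say so. That reading cannot apply to the ANCOVA, because four center means cannot support the listed covariates.

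Finally, the study is called a pilot. That supports reporting estimates with their limitations. It does not excuse an effectiveness test with the wrong error term.

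**Conclusion.** The concern holds, and it should be fixed before the data are analyzed. As written, the intervention test omits the level at which the intervention was assigned. Whenever the ICC of change is above zero, p-values are too small and intervals too narrow.

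For an ICC of 0.01 to 0.20, with 18 children per center and a two-sided 5% level, the true type I error is about 7% to 37%. A correct interval is about 1 to 2 SD either side, against about 0.47 SD on the child-level reading. Child-level covariates reduce the inflation slightly and do not remove it. Power for a 0.67 SD effect, 80% on the child-level reading, falls to 32%, 23%, 18% and 13% at the four ICCs when the test respects centers (2 v 2).

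The existence of the problem follows from the design. Its size rests on the assumed ICC.

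**What to change.** 1. Reconcile Specific Aims and Table 2 with the four centers in Recruitment Methods, and state the number of centers per arm. If there is one per arm, say that no test of the intervention is available.
2. In the Primary Endpoints and Data Analysis Plan section, name the center as the unit of inference. The simplest form adjusts children's changes for the covariates, averages them by center, and compares the center means between arms on 2 df. The alternative is a random center-by-time effect with df fixed at center level, or with a negative variance estimate allowed, so that a zero estimate does not restore about 70 df. A fixed center term will not do, because center is nested in arm. Ordinary sandwich standard errors are unreliable with four clusters.
3. Remove the child-level t-tests and chi-square tests as tests of the intervention; they can stay as description.
4. Report the effect, its interval and the ICC of change as pilot estimates. Word Aim 1 as estimating the effect, and limit the generalizability statement to what four selected centers support.

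**Cost.** Analysis and wording only, with no new data, children or centers. The real price is that the pilot will estimate the effect and is unlikely to confirm it. A confirmatory test would need more centers, which is a separate and costly decision.

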## B. Background

The significance of this project stems from Louisiana's prevalence of preschool obesity which is 60% higher than the national average: 13.8% of preschoolers in the state are obese compared to 8.4% nationally. Physical activity during early childhood is known to reduce the risk of being overweight or obese and therefore protect against the development of comorbidities, such as heart disease, diabetes, etc. later in life. Furthermore, at this young age the development of fundamental motor skills is highly related to physical activity and is therefore an important correlate to obesity. Despite assumptions that young children are active throughout the day, studies indicate that almost half of preschool play time is spent in sedentary activities. Over 80% of children spend some time in childcare settings by the age of 3 years, making childcare facilities an important venue for the promotion of fundamental motor skills and physical activity. As playground stenciling has been shown to increase moderate to vigorous physical activity (MVPA) during recess among older children, it is necessary to determine whether it has the same benefit for preschool aged children. Therefore, we propose to use a scientifically rigorous design (intervention vs. wait-list control) to determine the effectiveness of playground stenciling in Louisiana preschool aged children, a population burdened with an urgent, established obesity epidemic.

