Physical activity. Physical activity and time spent in moderate to vigorous physical activity will be measured by a triaxial accelerometer (Actigraph GT3X+, Actigraph of Ft. Walton Beach, FL). Children will be measured by the Actigraph for 24 hours per day for 7 days. Measurements with the Actigraph will

occur for one week at baseline (before stenciling) and follow-up (6-8 weeks after stenciling). The child will be outfitted with the accelerometer on an elasticized belt, on the right mid-axillary line, and parents will be provided a handout with instructions on when and how to place the device on their child. The Actigraph is one of the most common accelerometers used for scientific purposes, and the GT3X+ version provides extensive data on steps/day and time spent in various activity intensities. During wear weeks, study staff will check accelerometry wear during school hours to assess for compliance. The minimal amount of accelerometer data that will be considered acceptable is 4 days. Following the final day of data collection, the research team will verify the data for completeness using the most recent version of the ActiLife software (version 5.6 or higher; ActiGraph, Pensacola, FL) available at the time. Established cut-points will be used to classify sedentary behavior and physical activity such as the criteria of Pate et al. sedentary 0-799 counts per minute (CPM), light 800-1679 CPM, moderate 168-3367 CPM, and vigorous  $\geq$  3368 CPM. Other cutpoints may also be used for analyses.

The activPAL is a small device worn on the thigh by a small piece of tape. The monitors capture physical activity, sedentary time (including posture) and sleep. Children will be encouraged to wear the activPAL continuously for at least 72 hours, up to 96 hours (i.e., not take it off for any reason, including water activities [bathing, swimming] and sleeping). The monitor will be placed on the child on the first day they attend follow up assessments at the center and removed 4 days later at the center. Measurements with the activPAL will occur for 72-96 hours at follow-up only, and parents will be provided with instructions on use as well as additional tape for applying the device. ActivPALs will be distributed only to enrolled 4 year olds.

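### The baseline value of the outcome is not a listed covariate, raw changes are compared by t-test, and the plan does not ensure that covariate adjustment reaches the stencil effect

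*Combined protocol and SAP*

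**What the plan says.** Under Primary Endpoints and Data Analysis Plan, the endpoints are defined on the change scale: "The primary endpoints include change in MVPA and sedentary time during recess measured by accelerometry". Change in fundamental motor skills is secondary.

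Two between-arm analyses follow. The first is a model: "A repeated measures ANCOVA model will be used to test for effects of playground stenciling on each dependent continuous variable". Its outcomes are then listed in parentheses: MVPA and sedentary minutes per recess and per day in care, total daily MVPA, and total daily screen time. TGMD-3 is not among them. The second is a set of simple tests: "T-tests and chi-square tests will be used to determine whether changes in outcome variables were different between the intervention and control childcare centers".

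On adjustment the section says only: "Covariates will include age, sex, BMI z-score, and sociodemographic characteristics". Section A (Specific Aims) adds that the investigators "will include obesity as a covariate to control for differences in MVPA that may be due to weight".

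The plan does not say whether baseline is a response or a covariate in the model, which term is the stencil effect, or whether covariates are crossed with time. Table 2 schedules the ActiGraph, TGMD-3, height and weight at both baseline and follow-up, so baseline values are collected for all three key outcomes.

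**The concern.** A change score subtracts the whole baseline value, and with it the baseline measurement noise. When the groups are comparable, regressing follow-up on baseline is more precise for any pre-post correlation below 1. With at most 72 children, that precision is worth having, since it needs no new data.

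The second issue is whether the listed covariates do what the reader will expect. With two visits, the effect of interest is a difference in change. Whether age, sex, weight status and sociodemographics adjust that difference depends on how they enter the model, and this is left open. For motor skills the question does not arise: a t-test takes no covariates.

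Third, the text describes an intervention and a wait-list control but no random allocation. Children belong to intact centers, so the arms may differ at baseline. Change-score and baseline-adjusted estimates then answer the question differently, and an unspecified model leaves the choice open until the data are seen.

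**Working it through.** **Inputs.** From Recruitment Methods: "We aim to recruit up to 72 children (18 per center) between August 2018 and February 2019", at 4 centers; 4 × 18 = 72 reproduces the stated total. There are two visits (Procedures). The documents give no alpha, power, effect size, SD, pre-post correlation (rho) or ICC, so no power-based sample size can be reproduced, and rho and the ICC are assumed below. An equal 36:36 split is also assumed for the simulations.

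**1. Two visits make the repeated measures contrast a change score.** One data set of 72 children with complete data was simulated. Age was set to differ between arms and to have a different effect at each visit. Estimates of the stencil effect (SE) were:

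| Analysis | Estimate (SE) |
|---|---|
| t-test of change | 0.4917 (0.2166) |
| Arm × time, no covariates | 0.4917 (0.2166) |
| Arm × time, age, sex and BMI z as main effects | 0.4917 (0.2166) |
| Arm × time, covariates also crossed with time | 0.4524 (0.2069) |
| Change regressed on arm and covariates | 0.4524 (0.2069) |
| Follow-up on arm, baseline and covariates | 0.4265 (0.1662) |

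The first three rows are identical: a time-constant main effect adds the same amount to both visits and cancels. The fourth and fifth agree: covariate-by-time terms do adjust the change.

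The cancellation has limits. With 14 follow-up values removed, main-effect covariates moved the estimate from 0.394 to 0.404. Letting BMI z-score vary between visits moved it from 0.4917 to 0.4918.

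**2. Child-level precision.** Take the same SD (σ) at both visits and comparable groups.

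- Variance of change = 2σ²(1 − rho)
- Residual variance after baseline adjustment = σ²(1 − rho²)
- Ratio = (1 − rho²) / [2(1 − rho)] = (1 + rho)/2

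| Assumed rho | Variance ratio | SE ratio (square root) | Simulated variance ratio, 4,000 runs |
|---|---|---|---|
| 0.3 | 0.65 | 0.806 | 0.67 |
| 0.5 | 0.75 | 0.866 | 0.75 |
| 0.7 | 0.85 | 0.922 | 0.86 |
| 0.9 | 0.95 | 0.975 | not run |

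**3. Allowing for centers.** Let the change score have ICC = i, with 18 children per center, and assume that baseline adjustment reduces only the child-level part. At rho 0.5 the variance ratio is [18i + 0.75(1 − i)] / [18i + (1 − i)]. The number of centers per arm cancels.

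- i = 0.01: (0.18 + 0.7425)/(0.18 + 0.99) = 0.788; SE ratio 0.888, a fall of about 11%
- i = 0.05: (0.90 + 0.7125)/(0.90 + 0.95) = 0.872; SE ratio 0.934, a fall of about 7%
- i = 0.10: (1.80 + 0.675)/(1.80 + 0.90) = 0.917; SE ratio 0.957, a fall of about 4%

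Without clustering, the fall at rho 0.5 is 13%.

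**4. How far the two estimates can part.** If the arms differ at baseline by D, the change analysis subtracts D from the follow-up difference, and the baseline-adjusted analysis subtracts rho × D (equal SDs). The gap is (1 − rho)D. For D = 0.5 SD it is 0.35, 0.25 and 0.15 SD at rho 0.3, 0.5 and 0.7.

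**The case against.** **Covariates may already adjust the effect.** A reader might infer that the listed covariates do nothing to the stencil effect. The documents do not support that. They never say that covariates enter as main effects only, and a multivariate repeated measures fit in SAS, the software the plan names, crosses them with time. Nor does the term repeated measures ANCOVA strictly exclude baseline as a covariate. This objection stands: the defect is that the plan does not ensure adjustment, not that it rules it out. It does not help TGMD-3 as the text is written.

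**The obesity sentence may concern levels.** Section A speaks of differences in MVPA due to weight, and a main effect does address differences in level. BMI is also measured twice, so it is not strictly time-constant. Both points are fair. In the check, though, a BMI z-score that varied between visits hardly moved the contrast.

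**Baseline adjustment may be the wrong primary analysis.** If the centers differ stably rather than by chance, regression to the mean does not by itself bias the change comparison, and baseline adjustment can introduce bias. This stands. Neither estimator is guaranteed unbiased here, which is why both should be reported.

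**The gain is modest.** It depends on an unstated rho, shrinks with between-center variation, and is slight at rho 0.9. This stands too. Baseline adjustment does not remedy having only four centers.

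**Conclusion.** The concern holds in a limited form. Three things are firm: baseline is not a listed covariate; the simple tests act on raw change; and for TGMD-3 an unadjusted t-test of change is the only between-arm test described. For the ANCOVA outcomes, the plan leaves open whether the covariates reach the stencil effect. To say that they cannot would go beyond the text.

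The precision at stake is a child-level variance ratio of 0.65 to 0.85 for rho between 0.3 and 0.7. At rho 0.5, counting centers, this becomes a fall in standard error of about 4% to 11% over the assumed ICCs. These figures assume comparable groups, equal SDs at both visits and complete data. It would be wrong to turn the child-level ratios into an equivalent number of extra children, because that treats the 72 as independent.

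The choice of estimator also matters beyond precision. Without described random allocation, a 0.5 SD baseline difference moves the answer by 0.25 SD at rho 0.5. The change is worth making before the data are analysed.

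**What to change.** In Primary Endpoints and Data Analysis Plan:

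- For recess MVPA, recess sedentary time and TGMD-3, replace the unadjusted t-test of change with a model of the follow-up value on arm, the baseline value of the same outcome, age, sex, baseline BMI z-score and the poverty measure from the parent survey, with center accounted for.
- If the repeated measures form is kept, state that the stencil effect is the arm-by-time term and add covariate-by-time terms.
- Name in advance which estimate is primary, with the reason, and report the covariate-adjusted change-score estimate beside it.

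The cost is a few sentences and no new data. There are two downsides. The two estimates may disagree, and the report must then discuss why. Children without a valid baseline value, for example those below the 4-day accelerometer minimum, drop out of a complete-case baseline-adjusted model, whereas a likelihood-based repeated measures model can keep partial data. The plan should say how such children are handled.
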